5.5.5 Reporting of Serious Adverse Events (SAEs)

The collection of AEs and the expedited reporting of SAEs will start following receipt of the ICF and will continue until 60 days after last administration of study drug or the subject is determined to be a screen failure.

In the case of a SAE, the investigator must contact the sponsor by fax or email immediately (within 24 hours of awareness).

The investigator must complete and submit an SAE worksheet containing all information that is required by local and/or regional regulations to the sponsor by email or fax immediately (within 24 hours of awareness).

The SAE worksheet must be signed by a medically qualified investigator (as identified on Delegation of Authority Log). Signature confirms accuracy and completeness of the SAE data, as well as the investigator causality assessment including the explanation for the causality assessment.

For contact details, see [Section II Contact Details of Key Sponsor's Personnel]. Fax or email the SAE/Special Situations worksheet to:

Astellas Pharma Global Development – US
Pharmacovigilance
[contact] or [contact]
Email: [contact]

If there are any questions, or if clarification is needed regarding the SAE, please contact the sponsor's medical monitor/study physician or his/her designee [Section II Contact Details of Key Sponsor's Personnel].

Follow-up information for the event should be sent promptly (within 7 days of the initial notification).

Full details of the SAE should be recorded on the medical records, SAE/Special Situation Worksheet and on the eCRF.

The following minimum information is required:

- International study number/study number,
- subject number, sex and age,
- the date of report,
- a description of the SAE (event, seriousness criteria),
- causal relationship to the study drug (including reason), and
- the drug provided (if any).

The sponsor or sponsor's designee will medically evaluate the SAE and determine if the report meets the requirements for expedited reporting based on seriousness, causality and expectedness of the events (e.g., Suspected Unexpected Serious Adverse Reaction [SUSAR] reporting) according to current local/regional regulatory requirements in participating countries. The sponsor or sponsor's designee will submit expedited safety reports (e.g., IND

Safety Reports, SUSAR, Council for International Organizations of Medical Sciences [CIOMS] Form I) to Competent Authorities (CA) and concerned Ethics Committee (cEC) per current local regulations, and will inform the investigators of such regulatory reports as required. Investigators must submit safety reports as required by their IRB/local Independent Ethics Committee (IEC) within timelines set by regional regulations (e.g., EMA, FDA) where required. Documentation of the submission to and receipt by the IRB/local IEC of expedited safety reports should be retained by the site.

The sponsor will notify all investigators responsible for ongoing clinical studies with the study drug of all SUSARs, which require submission per local requirements.

The investigators should provide written documentation of IRB/IEC notification for each report to the sponsor.

The investigator may contact the sponsor's medical monitor/study physician for any other problem related to the safety, welfare or rights of the subject.

5.5.6 Follow-up of Adverse Events

All AEs occurring during or after the subject has discontinued the study are to be followed up until resolved or judged to be no longer clinically significant, or until they become chronic to the extent that they can be fully characterized by the investigator.

If after the protocol defined AE collection period [see Section 5.5.1 Definition of Adverse Event], an AE progresses to a SAE, or the investigator learns of any (S)AE including death, where he/she considers there is reasonable possibility it is related to the study drug treatment or study participation, the investigator must promptly notify the sponsor.

5.5.7 Monitoring of Common Serious Adverse Events

Not applicable for this study.

5.5.8 Special Situations

Certain special situations observed in association with the study drug, such as incorrect administration (e.g., wrong dose of study drug) are collected in the eCRF, as protocol deviation per [Section 8.3 Major Protocol Deviations] or may require special reporting, as described below. These special situations are not considered AEs, but do require to be communicated to Astellas as per the timelines defined below.

If a special situation is associated with, or results in, an AE, the AE is to be assessed separately from the special situation and captured as an AE in the eCRF. If the AE meets the definition of a SAE, the SAE is to be reported as described in [Section 5.5.5 Reporting of Serious Adverse Events] and the details of the associated special situation are to be included in the clinical description on the SAE worksheet.

The special situations are:

- Pregnancy
- Medication error, overdose and “off-label use”
- Misuse/abuse
- Occupational exposure
- Suspected drug-drug or other (e.g., food) interaction
- (Suspicion of) Transmission of infectious agent

Table 6 provides a list of special situations along with how each should be reported.

Table 6 Special Situations

Special Situation	Collected		
	SAE/Special Situations Worksheet	eCRF	Protocol Deviation [Section 8.3]
Overdose of the medicinal product(s) [Section 5.5.8.2]			X
Suspected misuse/abuse of the investigational medicinal product	X		X
Occupational exposure	X		
Suspected drug-drug or other interaction		X	
Off-label use of study drug	X		
Pregnancy	X	X	
Medication error		X	

eCRF: electronic case report form; SAE: serious adverse event

5.5.8.1 Pregnancy

If a female subject becomes pregnant during the study dosing period or within 30 days from the discontinuation of dosing, the investigator is to report the information to the sponsor according to the timelines in [Section 5.5.5 Reporting of Serious Adverse Events] using the Pregnancy Reporting Form and in the eCRF.

The investigator will attempt to collect pregnancy information on any female partner of a male subject who becomes pregnant during the study dosing period or within 30 days from the discontinuation of dosing and report the information to the sponsor according to the timelines in [Section 5.5.5 Reporting of Serious Adverse Events] using the Pregnancy Reporting Form.

The expected date of delivery or expected date of the end of the pregnancy, last menstruation, estimated conception date, pregnancy result and neonatal data etc., should be included in this information.

While pregnancy itself is not considered to be an AE or SAE, any pregnancy complication or termination (including elective termination) of a pregnancy is to be reported for a female study subject as an AE in the eCRF or SAE per [Section 5.5.5 Reporting of Serious Adverse

Events]. For (S)AEs experienced by a female partner of a male subject, (S)AEs are to be reported via the Pregnancy Reporting Form.

Additional information regarding the outcome of a pregnancy when also categorized as an SAE is mentioned below:

- "Spontaneous abortion" includes miscarriage, abortion and missed abortion.
- Death of a newborn or infant within 1 month after birth is to be reported as an SAE regardless of its relationship with the study drug.
- If an infant dies more than 1 month after the birth, it should be reported if a relationship between the death and intrauterine exposure to the study drug is judged as "possible" by the investigator.
- Congenital anomaly (including anomaly in miscarried fetus)

Unless a congenital anomaly is identified prior to spontaneous abortion or miscarriage, the embryo or fetus should be assessed for congenital defects by visual examination. (S)AEs experienced by the newborn/infant should be reported via the Pregnancy Reporting Form. Generally, follow-up will be no longer than 6 to 8 weeks following the estimated delivery date.

5.5.8.2 Medication Error, Overdose and "Off-label Use"

If a medication error, overdose or "off-label use" (i.e., use outside of what is stated in the protocol) is suspected, refer to [Section 8.3 Major Protocol Deviations]. Any associated (S)AEs are to be reported in the eCRF. If the AE meets the definition of a SAE, the SAE is also to be reported as described in [Section 5.5.5 Reporting of Serious Adverse Events] together with the details of the medication error, overdose and/or "off-label use".

In the event of suspected isavuconazonium sulfate overdose, the subject should receive supportive care and monitoring. At supratherapeutic doses (equivalent to isavuconazole 600 mg/day maintenance dose) evaluated in a thorough QT study in adults, there were proportionally more treatment-emergent adverse events (TEAEs) than in the therapeutic dose group (equivalent to isavuconazole 200 mg/day maintenance dose) for the following: headache, dizziness, paraesthesia, somnolence, disturbance in attention, dysgeusia, dry mouth, diarrhoea, oral hypoesthesia, vomiting, hot flush, anxiety, restlessness, palpitations, tachycardia, photophobia and arthralgia. Isavuconazole is not removed by hemodialysis.

There is no specific antidote for isavuconazole.

The medical monitor should be contacted as applicable.

5.5.8.3 Misuse/Abuse

If misuse or abuse of the study drug(s) is suspected, the investigator must forward the special situation worksheet to the sponsor by fax or email immediately (within 24 hours of awareness). Any associated (S)AEs are to be reported in the eCRF. If the AE meets the definition of a SAE, the SAE is also to be reported as described in [Section 5.5.5 Reporting of Serious Adverse Events] together with details of the misuse or abuse of the study drug(s).

5.5.8.4 Occupational Exposure

If occupational exposure (e.g., inadvertent exposure to the study drug of site staff while preparing it for administration to the subject) to the study drug occurs, the investigator must forward the Special Situation worksheet to the sponsor by fax or email immediately (within 24 hours of awareness). Any associated (S)AEs occurring to the individual associated with or resulting from the Special Situation are to be reported on the Special Situations worksheet.

5.5.9 Supply of New Information Affecting the Conduct of the Study

When new information becomes available necessary for conducting the clinical study properly, the sponsor will inform all investigators involved in the clinical study, as well as the regulatory authorities. Investigators should inform the IRB/IEC of such information when needed.

The investigator will also inform the subjects, who will be required to sign an updated ICF in order to continue in the clinical study.

5.5.10 Urgent Safety Measures

An urgent safety measure (USM) is an intervention, which is not defined by the protocol and can be put in place with immediate effect without needing to gain prior approval by the sponsor, relevant CA, IRB/IEC, where applicable, in order to protect study participants from any immediate hazard to their health and/or safety. Either the investigator or the sponsor can initiate an USM. The cause of an USM can be safety, product or procedure related.

5.5.11 Reporting Urgent Safety Measures

In the event of a potential USM, the investigator must contact the Astellas study physician (within 24 hours of awareness). Full details of the potential USM are to be recorded in the subject's medical records. The sponsor may request additional information related to the event to support their evaluation.

If the event is confirmed to be an USM the sponsor will take appropriate action to ensure the safety and welfare of the subjects. These actions may include, but are not limited to, a change in study procedures or study treatment, halting further enrollment in the trial, or stopping the study in its entirety. The sponsor or sponsor's designee will notify CA and cEC within the timelines required per current local regulations, and will inform the investigators as required. When required, investigators must notify their IRB/IEC within timelines set by regional regulations.

5.6 Test Drug Concentration

Plasma concentrations of isavuconazole will be analyzed to monitor the levels of isavuconazole in the subject population during treatment. For the purpose of this study, serial blood samples (approximately 1 mL) will be collected in 1-mL potassium ethylenediaminetetraacetic acid. Vacutainer tubes for each scheduled nominal time point on days 7, 14, 21, 42 and day 84 or EOT. The samples should ideally be drawn immediately prior to the dose of study drug, must be taken no earlier than 1 hour prior.

In addition to the above, 24-hour pharmacokinetic samples will be obtained on any day between day 14 and day 42, while the subject is still receiving study drug, for subjects who consent to participation in the 24-hour pharmacokinetic assessment. The goal is to achieve approximately 6 subjects in each age cohort by the time enrollment is completed for the study.

The intravenous pharmacokinetic samples will be obtained as follows:

1. within 1 hour prior to the start of the intravenous isavuconazonium sulfate infusion (this sample will be the same as the trough sample prior to dose if it coincides with scheduled days 14, 21 or 42);
2. immediately after the completion of the intravenous infusion (no more than 5 minutes after);
3. within 4 to 10 hours after the start of the intravenous infusion; and
4. within 16 to 24 hours after the start of the intravenous infusion (must be obtained before the start of the next infusion).

The oral pharmacokinetic samples will be obtained as follows:

1. within 1 hour prior to the next oral dose (this sample will be the same as the trough sample prior to dose if it coincides with scheduled days 14, 21 or 42);
2. 1 hour post dose (\pm 10 minutes);
3. 3 hours post dose (\pm 10 minutes);
4. 4 hours post dose (\pm 10 minutes);
5. within 6 to 8 hours (\pm 30 minutes) of study drug administration; and
6. 24 hours (within 1 hour before next study drug administration) after study drug administration.

No additional pharmacokinetic samples will be taken from IM subjects during days 85 to 180.

Immediately after each sample collection, gently invert the blood sample 8 to 10 times and place in an ice water bath. Within 1 hour of sample collection, centrifuge the blood sample(s) at 1200 g for 10 minutes at approximately 4°C in order to obtain plasma.

Plasma will be harvested and divided equally into 2 (primary and back-up) appropriately labeled storage tubes.

Store the plasma samples in a freezer set to maintain $-20^{\circ}\text{C} \pm 10^{\circ}\text{C}$ or lower immediately following centrifugation and separation.

Primary and back-up samples will be shipped separately to the bioanalytical laboratory.

5.7 Other Measurements, Assessments or Methods

Not applicable.

5.8 Total Amount of Blood

The total blood volume to be collected on subjects 1 to < 18 years of age for the study through day 84 or EOT should not be more than 45 mL. Table 7 provides the amount of blood drawn for each laboratory parameters and study visit for these subjects.

Table 7 Total Amount of Blood Drawn

Parameter	Study Visit						Total Volume
	Screening	Labs: Days 7, 28, 56 and 84 or EOT	Pharmacokinetics: Days 7, 14, 21, 42 and 84 or EOT	Days 3, 14, 21, 35, 42, 49, 63, 70 and 77	IV Pharmacokinetics: 24-hour Sampling Day Anytime Between Days 14 and 42	Oral Pharmacokinetics: 24-hour Sampling Day Anytime Between Days 14 and 42	
Hematology	2 mL	2 mL/visit (8 mL)	N/A	N/A	N/A	N/A	10 mL
Chemistry	2 mL	2 mL/visit (8 mL)	N/A	N/A	N/A	N/A	10 mL
Hepatic Panel	*	*	N/A	1 mL/visit (9 mL)	N/A	N/A	9 mL
Serum GM	2 mL	N/A	N/A	N/A	N/A	N/A	2 mL
Pharmacokinetics	N/A	N/A	1 mL/visit (5 mL)	N/A	1 mL/time point (4 mL)	1 mL/time point (7 mL)	9 mL or 12 mL
PT/INR	1 mL	1 mL/visit (4 mL)	N/A	N/A	N/A	N/A	5 mL
TOTAL	7 mL	20 mL	5 mL	9 mL	4 mL	7 mL	45 mL (IV 24-hr PK) -OR- 48 mL (Oral 24-hr PK)

EOT: end of treatment; GM: galactomannan; INR: international normalized ratio; IV: intravenous; N/A: not applicable; PK: pharmacokinetics; PT: prothrombin time

* Included with chemistry

The total blood volume to be collected on IM subjects 1 to < 18 years of age during the IM follow-up period should not be more than 15 mL. Table 8 provides the amount of blood drawn for each laboratory parameters for these subjects.

Table 8 Blood Drawn During IM Follow-up

Parameter	Study Visits Days 115, 145 and 180 or EOT	Approximate Total Volume
Hematology	2 mL/visit (6 mL)	6 mL
Chemistry	2 mL/visit (6 mL)	6 mL
Hepatic Panel	*	N/A
PT/INR	1 mL/visit (3 mL)	3 mL
TOTAL	15 mL	15 mL

*Hepatic panel to be drawn with chemistry panel.

INR: international normalized ratio; PT: prothrombin time

Regarding the protocol-specified clinical laboratory, if clinical safety laboratory results are already available, these data are sufficient for monitoring safety as per the protocol and must be recorded in the eCRF. In order to minimize blood draws, it is not necessary to draw an additional sample for the sole purposes of the clinical trial.

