1. within 1 hour prior to the start of the intravenous isavuconazonium sulfate infusion (this sample will be the same as the trough sample prior to dose, if it coincides with scheduled days 14, 21 or 42);
2. immediately after the completion of the intravenous infusion (no more than 5 minutes after);
3. within 4 to 10 hours after the start of the intravenous infusion; and
4. within 16 to 24 hours after the start of the intravenous infusion (must be obtained before the start of the next infusion).

Subjects receiving oral administration:

The 24-hour pharmacokinetic samples will be obtained for oral dosing as follows:

1. within 1 hour of next oral dose (this sample will be the same as the trough sample prior to dose, if it coincides with scheduled days 14, 21 or 42);
2. 1 hour post dose (\pm 10 minutes);
3. 3 hours post dose (\pm 10 minutes);
4. 4 hours post dose (\pm 10 minutes);
5. within 6 to 8 hours (\pm 30 minutes) of study drug administration; and
6. 24 hours post dose (within 1 hour before next study drug administration) after study drug administration.

No additional samples will be taken from IM subjects after day 84.

Throughout the study, safety and tolerability will be assessed by the recording of adverse events (AEs), vital signs, electrocardiograms (ECGs) and safety laboratory evaluations. This includes assessments at 14 days, 28 days and 56 days. All subjects will complete 2 follow-up visits. At the discretion of the investigator, follow-up visits may be conducted via telephone with the subject, the subject's parent or the subject's legal guardian, 30 and 60 days after the subject's day 84 (IA)/day 180 (IM) or EOT visit.

If subject discontinues study drug prior to day 84 or day 180, all EOT procedures must be completed. If subject continues to allow consent, end of study (EOS) information will be collected 30 and 60 days after EOT.

Inclusion/Exclusion Criteria:

Inclusion:

1. Institutional Review Board (IRB)-approved written informed consent and privacy language as required per national regulations (e.g., Health Insurance Portability and Accountability Act authorization) must be obtained from the subject's parent or legal guardian and, if required, subject's assent, prior to any study-related procedures (including withdrawal of prohibited medication, if applicable).
2. Male or female subject 1 year to < 18 years of age diagnosed with IA or IM. A positive diagnosis is defined as follows:

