2. Follow-up is to be completed 30 (\pm 7) and 60 days (\pm 7) post-last dose from day 84 or EOT for IA subjects, and may be performed via telephone at the discretion of the investigator.
3. Diagnosis must be completed within 10 days of first dose.
4. Height is to be collected at baseline only. Weight is to be taken at baseline and day 84 or EOT.
5. Vital signs are to be measured within 1 hour prior to and approximately 1 hour after the end of each infusion. No additional vital signs are needed on dosing days for oral administration.
6. 12-lead ECG will be performed prior to study drug administration on each scheduled day.
7. Record assessments that are performed during the study to document response to antifungal therapy (e.g., serum galactomannan, radiology, mycological tests, changes in clinical signs and symptoms and any surgical procedure).
8. Pharmacokinetic trough samples should ideally be drawn immediately prior to the next dose of study drug, but must be taken no earlier than 1 hour prior to the next dose on days 7, 14, 21, 42 and 84 or EOT.
9. For both intravenous and oral dosing: 24-hour pharmacokinetic samples will be obtained on any one day between day 14 and day 42, while the subject is still receiving study drug, for subjects who consent to participation in the 24-hour pharmacokinetic assessment. The intravenous pharmacokinetic samples will be collected as follows: within 1 hour prior to the start of the intravenous isavuconazonium sulfate infusion. This sample will be the same as the trough sample prior to dose, if it coincides with scheduled days 14, 21 or 42, and immediately after the completion of the intravenous infusion (no more than 5 minutes after); and within 4 to 10 hours after the start of the intravenous infusion and within 16 to 24 hours after the start of the intravenous infusion (must be obtained before the start of the next infusion).
The oral pharmacokinetic samples will be collected as follows: within 1 hour of the next oral dose (this sample will be the same as the trough sample prior to dose, if it coincides with scheduled days 14, 21 or 42); 1 hour post dose (\pm 10 minutes); 3 hours post dose (\pm 10 minutes); 4 hours post dose (\pm 10 minutes); within 6 to 8 hours (\pm 30 minutes) of study drug administration; and 24 hours (within 1 hour before next study drug administration) after study drug administration.
10. Clinical (safety) laboratory samples will be assessed by the local laboratory.

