5.3.2 Pharmacokinetic Assessment

Blood samples will be collected for pharmacokinetic analysis of isavuconazole as depicted in [Table 1 and Table 2 Schedule of Assessments]. Blood sample collection, handling and storage will be described in the laboratory manual.

Blood sampling for the analysis of trough levels will be obtained from all subjects. The samples should ideally be drawn immediately prior to the dose of study drug, but must be taken no earlier than 1 hour prior to the dose on days 7, 14, 21, 42 and 84 or EOT.

In addition to the above, 24-hour pharmacokinetic samples for intravenous or oral dosing will be obtained on any one day between day 14 and day 42, while the subject is still receiving study drug, for subjects who consent to participation in the 24-hour pharmacokinetic assessment. The goal is to achieve approximately 6 subjects in each age cohort by the time enrollment is completed for the study.

The 24-hour **intravenous** pharmacokinetic samples will be obtained as follows:

1. within 1 hour prior to the start of the intravenous isavuconazonium sulfate infusion (this sample will be the same as the trough sample prior to dose if it coincides with scheduled days 14, 21 or 42);
2. immediately after the completion of the intravenous infusion (no more than 5 minutes after);
3. within 4 to 10 hours after the start of the intravenous infusion; and
4. within 16 to 24 hours after the start of the intravenous infusion (must be obtained before the start of the next infusion).

The 24-hour **oral** pharmacokinetic samples will be obtained as follows:

1. within 1 hour of next oral dose (this sample will be the same as the trough sample prior to dose, if it coincides with scheduled days 14, 21 or 42);
2. 1 hour post dose (\pm 10 minutes);
3. 3 hours post dose (\pm 10 minutes);
4. 4 hours post dose (\pm 10 minutes);
5. within 6 to 8 hours (\pm 30 minutes) of study drug administration; and
6. 24 hours (within 1 hour before next study drug administration) after study drug administration.

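### Protocol Section 5.8 limits blood to 45 mL, but its Table 7 totals 48 mL with oral 24-hour PK sampling and counts seven oral samples where the protocol lists six

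*Protocol*

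**What the plan says.** Protocol Section 5.8 (Total Amount of Blood) sets one limit for all subjects aged 1 to under 18 years: blood drawn "for the study through day 84 or EOT should not be more than 45 mL". It makes no exception for route of administration or for 24-hour PK sampling.

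Table 7, which the section gives as the breakdown for these same subjects, ends in two alternative totals: 45 mL with intravenous 24-hour PK and "48 mL (Oral 24-hr PK"). The oral 24-hour PK cell reads "1 mL/time point (7 mL"), which implies seven samples.

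The oral 24-hour time points are listed in five places: the Synopsis, Table 1 footnote 9, and Sections 2.2.1, 5.3.2 and 5.6. Each list has six: predose, 1, 3 and 4 hours, 6 to 8 hours, and 24 hours. The sixth and last is worded "24 hours (within 1 hour before next study drug administration) after study drug administration" in Sections 5.3.2 and 5.6.

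The 24-hour sampling is optional, being "for subjects who consent to participation in the 24-hour pharmacokinetic assessment" (Section 5.3.2). The same section gives its planned size: "The goal is to achieve approximately 6 subjects in each age cohort". On overlap with the trough schedule, the predose entry says "this sample will be the same as the trough sample prior to dose if it coincides with scheduled days 14, 21 or 42" (Section 5.6, oral list).

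**The concern.** There are two separate inconsistencies. First, the text of Section 5.8 and its own table give different figures for the same subjects: a limit of 45 mL and a planned total of 48 mL. Second, the seven oral samples costed in Table 7 do not match the six samples that the procedures ask for. Neither 45 nor 48 mL is therefore the volume that the listed oral procedures add up to.

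A blood-volume limit in children is an operational safety figure that sites and ethics committees rely on. As written, a reader cannot tell which volume applies to a subject in oral 24-hour sampling. No endpoint, analysis set or estimate depends on it.

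**Working it through.** **Inputs (Table 7, mL)**

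| Column | Calculation | Volume |
|---|---|---|
| Screening | 2 hematology + 2 chemistry + 2 galactomannan + 1 PT/INR | 7 |
| Labs, days 7, 28, 56 and 84 or EOT | 4 × (2 + 2 + 1) | 20 |
| Trough PK, days 7, 14, 21, 42 and 84 or EOT | 5 × 1 | 5 |
| Hepatic panel, nine other days | 9 × 1 | 9 |
| Intravenous 24-hour PK | 4 × 1 | 4 |
| Oral 24-hour PK, as printed | 7 × 1 | 7 |

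**Step 1: reproduce the printed totals by column**

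- Without 24-hour PK: 7 + 20 + 5 + 9 = 41 mL
- Intravenous: 41 + 4 = 45 mL
- Oral as printed: 41 + 7 = 48 mL

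**Step 2: repeat by row** (hematology + chemistry + hepatic panel + galactomannan + PK + PT/INR)

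- Intravenous: 10 + 10 + 9 + 2 + 9 + 5 = 45 mL
- Oral as printed: 10 + 10 + 9 + 2 + 12 + 5 = 48 mL

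Rows and columns agree, so the table adds correctly on its own entries and 48 mL is not a misread figure. The problem is what went into the oral cell and the limit stated above the table.

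**Step 3: use the six listed oral samples**

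The intravenous cell (4 mL) matches the four listed intravenous samples, so the table's convention is 1 mL per listed time point. Section 5.6 also puts a PK sample at approximately 1 mL. Six oral samples are then 6 mL.

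- By column: 41 + 6 = 47 mL
- By row, with PK 5 + 6 = 11: 10 + 10 + 9 + 2 + 11 + 5 = 47 mL

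**Step 4: allow for a shared trough**

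If the predose sample is also the day 14, 21 or 42 trough, 1 mL is saved: 47 − 1 = 46 mL. No more than one trough can be shared, because the ±2-day windows around days 14, 21 and 42 are not adjacent and the 24-hour series spans only two consecutive days.

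**Step 5: compare with 45 mL**

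| Full oral schedule | Total | Excess | Excess as share of 45 mL |
|---|---|---|---|
| As printed, seven samples | 48 mL | 3 mL | 3/45 = 6.7% |
| Six samples | 47 mL | 2 mL | 2/45 = 4.4% |
| Six samples, shared trough | 46 mL | 1 mL | 1/45 = 2.2% |

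**Step 6: who is affected**

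The goal of about 6 subjects in each of two age cohorts gives about 2 × 6 = 12 subjects in 24-hour sampling over both routes. Only those sampled while on oral drug are affected. Oral dosing is restricted to subjects aged at least 6 years and weighing at least 12 kg, so children aged 1 to under 6 are not affected.

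**The case against.** The strongest case on the other side is that this is editorial. Several points support that view.

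- The limit is phrased as a recommendation, and PK volumes are approximate.
- The totals assume the full schedule. Safety laboratory draws make up 10 + 10 + 9 + 5 = 34 mL of it, and Sections 5.4.2 and 5.8 allow results already available to replace them. Treatment may also end early on a successful outcome. A given subject may well stay within 45 mL.
- Table 7 shows 45 and 48 mL side by side, so the higher oral figure is not hidden.
- Every sampling list says six, so sites have no instruction to draw a seventh.
- At the minimum oral weight of 12 kg, a 2 mL excess is 2/12 = 0.17 mL/kg over the treatment period.

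All of this stands as a limit on the practical effect. None of it reconciles the printed figures: the reuse of results is conditional and does not change the planned totals, and the section still states 45 mL and plans 48 mL. The amendment attachment does not explain the difference, since its entry for this table only renumbers it and adds an abbreviation.

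One caution about the remedy is fair. The documents do not say outright which count was intended. Five matching lists make six very likely, but the sponsor should confirm it.

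**Conclusion.** The concern holds, as a minor inconsistency. The stated limit is 45 mL, the table plans 48 mL for oral 24-hour PK subjects, and the listed procedures add to 47 mL, or 46 mL with a shared trough. Correcting the sample count alone does not remove the conflict. The intravenous schedule meets the limit exactly and the schedule without 24-hour PK is 4 mL below it.

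This rests on 1 mL per PK sample, six oral samples as intended, and the full schedule through day 84. The figures are totals of the items in Table 7 only. The table gives no volume for serum pregnancy tests, where a site uses serum rather than urine, or for repeat liver tests after an abnormal result, so they are not upper bounds for any one subject.

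**What to change.** Confirm that six oral samples are intended. Then change four oral entries in Table 7 together, so that rows and columns still agree:

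1. Oral 24-hour PK cell: 7 to 6 mL.
2. PK row total for oral: 12 to 11 mL.
3. TOTAL row under the oral 24-hour column: 7 to 6 mL.
4. Overall oral total: 48 to 47 mL.

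If the third entry is left at 7, the column sum stays at 7 + 20 + 5 + 9 + 7 = 48 mL beside a stated 47 mL.

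Then settle the limit in one of two ways. Either state in Section 5.8 a 47 mL limit for subjects in oral 24-hour PK sampling, with the reason it is acceptable, or remove 2 mL from their schedule so that 45 mL holds. Requiring the 24-hour series to fall on a scheduled trough day would supply 1 mL of that, leaving 1 mL to find.

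Check that the consent form, which was not available for this review, gives the same figure. The cost is small: four table entries, one sentence in Section 5.8 and the consent-form check.
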